An observational clinical cohort analysis utilizing prospectively collected electronic medical record (EMR) data obtained from the OPERA® Observational Database will be used to address the study objectives. Subjects will be included from 01AUG2013 through 31DEC2017 and observed through 31DEC2018. HIV-1, ART-experienced patients who are at least 18 years of age and have been prescribed a core agent of interest for the first time will be included.

Endpoints & Outcomes:

- Primary outcomes:
 - o BMI (continuous and categories) and change in BMI (continuous)
 - Weight (continuous) and change in weight (continuous)
 - Total cholesterol, HDL, LDL and triglycerides (continuous and NCEP ATPIII categories)
 - Lipodystrophy diagnoses

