6. BACKGROUND AND RATIONALE

6.1. Background

Highly active antiretroviral therapy (ART) has changed human immunodeficiency virus (HIV) infection from a fatal illness to a chronic disease [1, 2]. Since the mid-1990's, regimens containing multiple antiretroviral drugs from at least two classes have been the standard of care in HIV treatment [3]. Combination therapy presents multiple barriers to viral replication and limits the development of drug-resistant mutations [3]. Integrase strand transfer inhibitors (INSTI) are the newest tool for prolonging survival and improving quality of life for people with HIV [4]. This class of medications includes raltegravir (RAL), elvitegravir (EVG), dolutegravir (DTG) and bictegravir (BIC). INSTIs appear to result in a more rapid decline in viral load and higher increases in CD4 counts when compared to protease inhibitors (PI) or efavirenz (EFV) based regimens [5-12].

Body composition has been a concern for patients with HIV since the initial manifestations of severe muscle wasting in the pre-ART era [13-16]. However, these concerns have evolved over time as studies have observed increases in weight among people living with HIV since the introduction of ART [17-19]. Lipodystrophy was associated with primarily older ART regimens but is still observed with some regimens containing newer agents including PIs such as darunavir (DRV) or atazanavir (ATV), INSTIs such as RAL, and non-nucleoside reverse transcriptase inhibitors (NNRTI) such as rilpivirine (RPV) [20-23].

Apart from irregular body fat deposition, weight gain was attributed to an improvement in health initially, especially among those severely immunocompromised. More recently, it has been appreciated that obesity and body mass index (BMI) have been increasing in HIV populations over time both before the initiation of ART and after [19]. In a sample of 14,084 patients living with HIV in the North American AIDS Cohort Collaboration on Research and Design (NA-ACCORD), the percentage of patients who were obese at ART initiation increased from 9% to 18% between 1998 and 2010 [17]. In the Swiss HIV Cohort Study, overweight/obesity prevalence increased from 13% in 1990 to 38% in 2012 [24].

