 - Severe dyslipidemia: ≥ 4.1 to < 4.9 mmol/L or ≥ 160 to < 190 mg/dl
 - Very severe dyslipidemia: ≥ 4.9 mmol/L or ≥ 190 mg/dl
- HDL levels¹
 - Normal: \geq 1.54 mmol/L or \geq 60 mg/dl
 - Borderline Abnormal: ≥ 1.03 to < 1.54 mmol/L or ≥ 40 to < 60 mg/dl
 - Dyslipidemia: < 1.03 mmol/L or < 40 mg/dl

¹ Cut-offs obtained https://www.nhlbi.nih.gov/files/docs/guidelines/atp3xsum.pdf

- Triglycerides levels¹
 - Normal: < 1.7 mmol/L or <150 mg/dl

 - Borderline Abnormal: \geq 1.7 to < 2.25 mmol/L or \geq 150 to < 200 mg/dl
 - Dyslipidemia: ≥ 2.25 to < 5.64 mmol/L or ≥ 200 to < 500 mg/dl
 - Severe dyslipidemia: ≥ 5.64 mmol/L or ≥ 500 mg/dl
- 3. Lipodystrophy:
 - Existing lipodystrophy: diagnosis of lipodystrophy within 12 months prior to or on index date
 - New lipodystrophy: new diagnosis of lipodystrophy at 6, 12, or 24 months after core agent initiation

A diagnosis of lipodystrophy will be identified in the EMR by searching for diagnosis codes and text consistent with lipodystrophy, lipohypertrophy, lipoaccumulation, hyperadiposity, or lipoatrophy.

Baseline	Follow-up	
Underweight (BMI: <18.5)	Underweight (BMI: <18.5)	
	Normal weight (BMI: 18.5 – 24.9)	
	Overweight (BMI: 25.0 – 29.9)	
	Obese (BMI: ≥30)	
Normal weight (BMI: 18.5 – 24.9)	Underweight (BMI: <18.5)	
	Normal weight (BMI: 18.5 – 24.9)	
	Overweight (BMI: 25.0 – 29.9)	
	Obese (BMI: ≥30)	
Overweight (BMI: 25.0 – 29.9)	Underweight (BMI: <18.5)	
	Normal weight (BMI: 18.5 – 24.9)	
	Overweight (BMI: 25.0 – 29.9)	
	Obese (BMI: ≥30)	
Obese (BMI: ≥30)	Underweight (BMI: <18.5)	
	Normal weight (BMI: 18.5 – 24.9)	
	Overweight (BMI: 25.0 – 29.9)	
	Obese (BMI: ≥30)	

Table 1. Changes in BMI categories

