8.5.1. Analysis of primary objectives

Baseline descriptive analyses of demographic and clinical characteristics

Descriptive statistics will be conducted for patients prescribed a core agent of interest between 01AUG2013 and 31DEC2017. All baseline covariates listed in sections 8.3.2. and 8.3.3. will be described, as well as baseline BMI, weight, lipodystrophy and lipid panels; medians and interquartile ranges for continuous variables and counts and percentages for categorical variables will be provided. Pairwise comparisons between DTG and each of the other core agent groups will be evaluated by p-values calculated from the Pearson Chi-Square test for categorical variables. The Fisher's exact test will be used to compare frequencies with few events. The Wilcoxon Rank Sum test will be used to calculate p-values for continuous variables.

Description of follow-up levels of total cholesterol, HDL, LDL, triglycerides, weight and BMI

Lipids (total cholesterol, HDL, LDL, triglycerides), weight and change in weight, and BMI and change in BMI will be assessed continuously and compared between patients for each core agent at 6,12, and 24 months after initiation. BMI and lipids will also be assessed categorically, as the proportion of patients in each BMI and lipid category and the proportion of patients changing categories of BMI (see section 8.3.2 for a definition of changes in categories). Given that the data reflect routine clinical care, not all patients will have the lab values of interest at each time point. The denominator for proportions will be patients tested, excluding those with missing values. Pairwise comparisons will be performed using Pearson Chi-Square test or Fisher's exact test for categorical variables and Wilcoxon Rank Sum test for continuous variables.

Description of existing lipodystrophy at core agent initiation and new diagnoses of lipodystrophy

Existing lipodystrophy will be assessed as the proportion of patients diagnosed with lipodystrophy 12 months prior to or on the index date among patients initiating each core agent of interest. New cases of lipodystrophy will be assessed as the proportion of patients who develop lipodystrophy at 6,12, or 24 months after initiation among patients without lipodystrophy at baseline. Pairwise comparisons will be performed using Pearson Chi-Square test or Fisher's exact test.

Association between type of core agent initiation and changes in BMI:

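### The lipodystrophy outcome pools fat gain and fat loss in one yes/no diagnosis, so its comparison between agents has no direction

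*Protocol*

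**What the plan says.** The abstract (section 3) lists "Lipodystrophy diagnoses" among the primary outcomes and names them, with BMI and lipids, as a way of describing weight outcomes. Section 6.2 says the analysis is meant to support evaluation of a weight-gain signal for DTG.

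Section 8.3.2 finds cases through diagnosis codes and "text consistent with lipodystrophy, lipohypertrophy, lipoaccumulation, hyperadiposity, or lipoatrophy". It then defines two states only. The baseline state reads: "Existing lipodystrophy: diagnosis of lipodystrophy within 12 months prior to or on index date". The follow-up state is a case newly diagnosed by the 6-, 12- or 24-month time point, again of any type.

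Section 8.5.1 summarises new cases as "the proportion of patients who develop lipodystrophy at 6,12, or 24 months after initiation among patients without lipodystrophy at baseline". It adds: "Pairwise comparisons will be performed using Pearson Chi-Square test or Fisher's exact test". Neither section separates the types. Stratifying by ART-naïve and ART-experienced does not restore direction within a stratum.

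**The concern.** Lipohypertrophy, lipoaccumulation and hyperadiposity describe fat gain, and lipoatrophy describes fat loss. For a study prompted by a weight-gain signal these have opposite meanings, yet each counts as the same event.

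Elsewhere the protocol keeps direction. Changes in BMI and weight are signed differences, Table 1 shows movement up and down between BMI categories, and section 8.3.3 lists drugs linked to weight gain apart from those linked to weight loss. Lipodystrophy is the exception.

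The pooled rule also sets the risk set. Any type recorded at baseline removes the patient from the count of new cases of every type. What is at stake is whether the lipodystrophy comparison can be interpreted: a difference could come from either process, and the absence of one could hide opposing processes.

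**Working it through.** **Inputs.** The case definition, the baseline window and the risk set come from sections 8.3.2 and 8.5.1. The protocol gives no lipodystrophy rate, no share by type and no sizing for this outcome; Table 2 in section 8.5.3 concerns the BMI regression. There is thus no stated figure to reproduce, and every rate below is an assumption for illustration.

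**Step 1: what pooling does to a proportion.** Let g be the proportion with new fat gain and a the proportion with new fat loss. If no patient has both, the pooled proportion is g + a. For agents 1 and 0:

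- difference = (g1 − g0) + (a1 − a0)
- ratio = (g1 + a1)/(g0 + a0)

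If a1 = a0, the difference stays at g1 − g0 and a ratio above 1 moves towards 1. If a1 and a0 differ, the difference itself changes.

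**Step 2: equal atrophy.** Assume fat gain of 1.0% v 0.5%, a ratio of 2.0 and a difference of 0.5 points.

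- Add 0.5% to both: 1.5% v 1.0%, ratio 1.5, difference 0.5 points.
- Add 1.0% to both: 2.0% v 1.5%, ratio 2.0/1.5 = 1.33, difference 0.5 points.

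**Step 3: power, and unequal atrophy.** Assume fat gain of 2% v 1%, 2000 patients per group and two-sided alpha 0.05. With p̄ = (p1 + p0)/2,

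power = Φ{[|p1 − p0|√n − 1.96√(2p̄(1 − p̄))] / √(p1(1 − p1) + p0(1 − p0))}.

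- Fat gain alone: (0.01 × 44.72 − 0.3369)/0.1718 = 0.642, so power is 74%.
- Plus 1% fat loss in both groups: (0.4472 − 0.4327)/0.2207 = 0.066, so power is 53%.
- Plus fat loss of 0.5% v 1%: (0.2236 − 0.4111)/0.2097 = −0.894, so power is 19%.

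| Fat loss | Pooled | Ratio | Difference (points) | Power at 2000 per group | Per group for 80% |
|---|---|---|---|---|---|
| 0% v 0% | 2% v 1% | 2.0 | 1.0 | 74% | 2319 |
| 1% v 1% | 3% v 2% | 1.5 | 1.0 | 53% | 3826 |
| 0.5% v 1% | 2.5% v 2% | 1.25 | 0.5 | 19% | 13809 |
| 0% v 1% | 2% v 2% | 1.0 | 0 | 5% (alpha only) | none suffices |
| 0% v 2% | 2% v 3% | 0.67 | −1.0 | 53%, wrong direction | not applicable |

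Every row has the same true doubling of fat gain. Only the atrophy rates change.

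**Step 4: the risk set.** Take a patient with lipoatrophy recorded eight months before index and a first lipohypertrophy diagnosis six months after. The first record makes lipodystrophy existing at baseline, so the patient leaves the denominator and the later diagnosis is not counted. Had the lipoatrophy been recorded only before the 12-month window, the patient would stay in and the later diagnosis could count.

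**The case against.** The strongest reply is that little depends on this outcome. Its objective is descriptive, it has no adjusted model or sizing, and it is absent from the secondary objective. The background also treats irregular fat deposition as distinct from general weight gain. All of that stands and limits the weight of the point.

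Four stronger readings are tempting, and the documents do not support them:

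- A reader might infer that pooling can mask the weight-gain effect under evaluation. It cannot: that question is addressed through change in BMI, and both BMI and weight changes are signed.
- A reader might infer that any past lipoatrophy bars a patient from ever counting as a new fat-gain case. The exclusion reaches only diagnoses in the 12 months up to index, and the number affected is not given.
- A reader might infer that many cases in ART-experienced patients are atrophy left over from older drugs. Section 6.1 says only this: "Lipodystrophy was associated with primarily older ART regimens but is still observed with some regimens containing newer agents". It does not name the type.
- A reader might infer that pooling shrinks the real difference. With equal atrophy the difference in proportions is unchanged; only the ratio and power fall. The null and reversed cases need atrophy to differ by agent, which no section shows.

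It can also be said that tabulation by type is a detail for an analysis plan, and nothing in the protocol forbids it. But the protocol itself fixes the case definition, the risk set, the summary and the test, and all four are pooled. The comment is on a stated rule, not on a missing detail.

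**Conclusion.** The concern holds for the lipodystrophy result alone. As defined, that result has no direction, so a higher, equal or lower pooled proportion on one agent says nothing definite about fat accumulation. Patients with lipoatrophy recorded in the baseline window are also lost as possible new accumulation cases.

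The size cannot be derived from the protocol. It runs from nothing, if atrophy is absent, through loss of power at an unchanged risk difference, if atrophy is equal across agents, to a null or reversed comparison, if atrophy differs by agent. These statements rest on assumed rates and on the simplification that no patient has both types. This is a cheap improvement to one primary descriptive outcome and does not threaten the main BMI analysis.

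**What to change.** In sections 8.3.2 and 8.5.1:

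1. Classify each hit, where the code or text allows, as fat accumulation (lipohypertrophy, lipoaccumulation, hyperadiposity), fat loss (lipoatrophy), both, or unspecified.
2. Report existing cases by type. Report new cases of each type among patients without that type in the 12-month baseline window, and state how patients with an unspecified baseline diagnosis are handled.
3. Keep the pooled proportion and its planned comparison beside these, so that nothing planned is lost. There is no need to replace the outcome with a new endpoint.

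The cost is classification and programming, with no new data collection. The protocol does not say that hits are stored by term or that the codes carry a type, so this should be checked first. The drawbacks are smaller counts per type and an unspecified group, possibly large, that cannot be assigned. Even then, reporting its size would show how far the pooled result can be interpreted.

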8.3.3. Study covariates

The following patient demographic and clinical characteristics will be assessed when first entering the healthcare setting at one of the designated clinics or within the 12-month baseline period preceding the index date. Data from the visit closest to the index date will be used for analysis.

Demographic variables

- Age
 - Continuous (years)
 - Categorical:
 - i. 18-25 years old
 - ii. 26-49 years old
 - iii. 50+ years old
- Gender
- Race/ethnicity (Black non-Hispanic, Black Hispanic, non-Black Hispanic, American Indian, Native Hawaiian, Pacific Islander, Asian, White non-Hispanic)
- History of injection drug use (yes/no)
- Marital status (e.g., single, married/domestic partnership, widowed, divorced/separated, unknown)
- Geographic region (i.e., Northeast, Midwest, South, West)
- Payer type (i.e. Medicaid, Medicare, commercial insurance, AIDS drug assistance programs (ADAP)/Ryan White, cash, no payer information available)

Virologic variables

- HIV viral load at baseline
 - Continuous (copies/mL and log₁₀ copies/mL)
 - Categorical (naïve):
 - Low (<10,000 copies/mL)
 - Moderate (≥10,000 to <100,000 copies/mL)
 - High (≥100,000 copies/mL)
 - Missing
 - Categorical (experienced):
 - Undetectable (<50 copies/mL)
 - Suppressed (≥50 to <200 copies/mL)
 - Viremic (≥200 copies/mL)
 - Missing

Immunologic variables

- CD4 cell count at baseline
 - Continuous (cells/μL)
 - Categorical:
 - High (CD4 > 500 cells/μL)
 - Moderately High (CD4 count >350 to ≤500 cells/µL)
 - Moderate (CD4 count >200 to ≤350 cells/µL)
 - Moderately Low (CD4 count >50 to ≤200 cells/µL)
 - Low (CD4 count ≤50 cells/µL)
 - Missing

Clinical variables

- Year of ART initiation
- Length of previous regimen (ART-experienced patients only)
- Time between index and end of follow-up (months)
- AIDS defining illnesses at baseline
- Mortality Risk (VACS Mortality Index)
- Comorbid conditions occurring on or before the index date (including T2DM and thyroid disease)
- HCV and HBV co-infection
- Blood pressure
- Concomitant medications associated with weight gain [31, 32] (these medications will be characterized and considered for inclusion in the statistical adjustment set)
 - Definite:
 - i. Antipsychotics and mood stabilizers
 - chlorpromazine, clozapine, haloperidol, lithium, olanzapine, valproic acid, risperidone, quetiapine
 - ii. Antidepressants
 - phenelzine, tranylcypromine, citalopram, amitriptyline, nortriptyline, mirtazapine, paroxetine
 - iii. Antihyperglycemics
 - 1. insulin, chlorpropamide, gliclazide, glyburide, pioglitazone, rosiglitazone, repaglinide, tolbutamide, rosiglitazone
 - iv. Antihypertensives
 - 1. atenolol, metroprolol
 - v. Corticosteroids

- 1. cortisone, prednisolone, prednisone, methylprednisolone, hydrocortisone
- vi. Hormones
 - 1. human growth hormone/somatropin
 - 2. medroxyprogesterone
- vii. Anticonvulsants
 - 1. Gabapentin, valproic acid/sodium valproate, carbamazepine
- viii. Antihistamines
 - 1. cyproheptadine
- Concomitant medications associated with weight loss (these medications will be characterized and considered for inclusion in the statistical adjustment set)
 - Definite:
 - i. Anti-infectives
 - 1. metronidazole, amphotericin, atovaquone, pyrimethamine, ethionamide
 - ii. Antineoplastics
 - aldesleukin and interleukin-2, capecitabine, carboplatin, cytarabine, dacarbazine, fluorouracil, hydroxyurea, imatinib, irinotecan, methotrexate, vinblastine sulphate, vinorelbine tartrate
 - iii. Bronchodilators
 - 1. salbutamol sulphate, theophylline
 - iv. Cardiovascular drugs
 - 1. amiodarone, acetazolamide, hydralazine HCl, quinidine
 - v. Stimulants
 - 1. methylphenidate HCl, phentermine
 - vi. Antidepressants
 - 1. fluoxetine, bupropion
 - vii. Anticonvulsants
 - 1. topiramate
 - viii. Antihyperglycemics
 - 1. exenatide, liraglutide, semaglutide
 - ix. Anti-inflammatories
 - 1. sulphasalazine
 - x. Weight loss drugs
 - 1. bupropion-naltrexone, liraglutide, lorcaserin, orlistat, phentermine-topiramate
 - xi. Dementia treatment
 - 1. galantamine, rivastigmine

• Number of classes of ART experience prior to baseline (ART-experienced patients only)

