In 1,809 ART-naïve patients randomized to ATV/ritonavir (r)/TDF/FTC, DRV/r/TDF/FTC, or RAL/TDF/FTC, weight increased on average by 3.8 kg and BMI by 1.3 kg/m² over 96 weeks [30]. Adjusted logistic regression with multiple imputation was performed to predict severe weight gain (i.e. \geq 10% increase in weight if \geq normal BMI at baseline; \geq overweight at 96 weeks if underweight at baseline) and severe BMI increase (i.e. increase of one or more BMI categories at 96 weeks if \geq normal baseline BMI; \geq overweight at 96 weeks if underweight at baseline). Compared to RAL, patients prescribed ATV/r were less likely to experience a severe weight increase (aOR: 0.72, 95% CI: 0.53, 0.99) and those prescribed DRV/r were less likely to experience a severe BMI increase (aOR: 0.73; 95% CI:0.53, 0.99) [30]. The relative impact on weight gain of most common core ART agents has yet to be determined.

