6.2. Rationale

Disentangling weight gain due to improved health status from weight gain due to an undesired effect of therapy requires an assessment of a large number of patients who may be progressing toward a stable health status or in whom a stable health status has been achieved and maintained.

Following raised disproportionality analysis (DPA) scores for both DTG and DTG/ABC/3TC detected through the routine pharmacovigilance, clinical trial data, spontaneous case reports, and published studies were reviewed. The cumulative evidence could not rule out an association between DTG exposure and weight gain, leading to a recommendation for a label change indicating weight gain as an uncommon ADR. This analysis, utilizing data from a large real-world population of treated HIV patients, will provide additional information to support the signal evaluation.

7. **RESEARCH QUESTION AND OBJECTIVE(S)**

Primary:

- Among new users of DTG, RPV, RAL, BIC*, EVG/c and DRV(/r/c): To describe BMI categories, weight, lipid levels (e.g. total cholesterol, HDL, LDL, triglycerides), and lipodystrophy at core agent initiation and at 6,12, and 24 months after core agent initiation, stratified by ART- naïve and ARTexperienced.
- Among ART-experienced new users of DTG vs. RPV, RAL, BIC*, EVG/c or DRV (/r/c): To estimate the association between specific core agent initiation and changes in BMI at 6, 12, and 24 months after core agent initiation.

Secondary:

 Among ART-experienced patients who were suppressed at switch (stable switch) to DTG, RPV, RAL, BIC*, EVG/c, or DRV(/r/c): To describe BMI categories, weight, and lipid panels levels (e.g. total cholesterol, HDL, LDL) at core agent initiation, and at 6,12, and 24 months after core agent initiation

*Due to recent approval and more limited potential follow-up, patients taking BIC will be included for 6-month outcomes only.

8. **RESEARCH METHODS**

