8.2. Study Population and Setting

The analysis population will be identified from the OPERA Observational Database according to the inclusion criteria defined below.

Primary population

1) A diagnosis of HIV-1, a positive HIV-1 Western Blot, or a positive HIV-1specific ELISA; and a detectable HIV-1 viral load test

- 2) At least 18 years of age at the index date
- 3) Male or female patients
- 4) Prescribed DTG, RPV, RAL, BIC, EVG/c and DRV(/r/c) as part of a 3-drug regimen for the first time between 01AUG2013 and 31DEC2017
- 5) Not exposed to >1 core agent of interest concurrently

Subjects with the following criteria will be excluded from the study sample:

- 1) HIV-negative
- A diagnosis of HIV-2, a positive HIV-1/HIV-2 Multispot, a positive HIV-2specific ELISA, a positive HIV-2 Western Blot or a detectable HIV-2 viral load test
- 3) Women who are considered pregnant at the index date
- 4) Transgender patients (potential for weight changes due to hormone use)

Secondary population

The study population for the secondary objectives will be a subset of the primary study population meeting the following additional inclusion criteria:

- Patients switching to DTG, RPV, RAL, BIC, EVG/c or DRV(/r/c) as part of a 3-drug regimen for the first time between 01AUG2013 and 31DEC2017 (excluding ARTnaïve patients)
- Patients with a viral load <200 copies/mL at last viral load test prior to switch to core agent of interest

The descriptive primary objective (1) will be stratified by prior ART exposure (ART-naïve and ART-experienced. The primary objective assessing association between core agent and BMI change (2), and the secondary objective will be restricted to ART-experienced patients. ART-experienced will be defined as history of ART prior to initiation of the core agent of interest, or a baseline viral load of <1000 copies/mL.

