8.3. Variables

8.3.1. Exposure definitions

Exposures

• First exposure to any core agent of interest (DTG vs. RPV, RAL, BIC, EVG/c or DRV(/r/c)), after inclusion in the OPERA database. Prior exposure to other core agents of interest is not allowed after inclusion in the OPERA database.

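### The adjusted BMI comparison in ART-experienced patients is open to residual confounding by the regimen left behind and by restarting rather than directly switching ART

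*Protocol*

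**What the plan says.** All references are to the protocol.

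- **Prior-ART covariates (8.3.3).** There are three: "Year of ART initiation", "Length of previous regimen (ART-experienced patients only") and "Number of classes of ART experience prior to baseline (ART-experienced patients only"). They give a date, a duration and a count. None identifies the agent or class stopped, or shows a gap before the index date.
- **Who is ART-experienced (8.2).** "ART-experienced will be defined as history of ART prior to initiation of the core agent of interest, or a baseline viral load of <1000 copies/mL". Being on treatment at index is not a condition. Viral suppression below 200 copies/mL is required only for the secondary population, whose objective is descriptive.
- **Limit on earlier core agents (8.3.1).** "Prior exposure to other core agents of interest is not allowed after inclusion in the OPERA database".
- **Outcome (8.3.2).** BMI change is measured from a baseline weight taken in the 3 months up to and including the index date.
- **Adjustment (8.5.1).** The variables chosen in advance include age, sex, race/ethnicity, comorbidity, weight-related co-medication, and change in viral load and CD4 count. No prior-ART variable is named. Other factors may be added if the descriptive analyses show them to be confounders. Those analyses are stated to cover the covariates of 8.3.2 and 8.3.3.
- **Aim (6.2).** The rationale sets the task as "Disentangling weight gain due to improved health status from weight gain due to an undesired effect of therapy".

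**The concern.** For a direct switcher, the baseline weight is a weight on the old regimen, so the later change reflects the new agent relative to the old one. If patients leaving a given class tend to be moved to a particular new agent, a difference that belongs to the old regimens can appear as a difference between the new ones.

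A patient restarting after an interruption may regain weight through recovery. If restarters are unevenly spread over the core agents, that regain is credited to the agent they happen to start. Length of previous regimen does not separate the two kinds of patient, because it measures how long the last regimen ran and not when it ended.

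The second primary objective is the protocol's only adjusted comparison between agents, and it is meant to support a safety signal evaluation. A bias could run in either direction, hiding a difference or creating one.

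**Working it through.** **1. The plan's own figure.** Section 8.5.3, Table 2, gives the sample size for 80% power. Inputs are 4 exposure degrees of freedom, 10 covariates and partial correlation ρ from 0.02 to 0.20. The protocol states no alpha; 0.05 is assumed. With f² = ρ²/(1 − ρ²), noncentrality f²·N and error degrees of freedom N − 4 − 10 − 1, the noncentral F distribution reproduces all ten rows exactly, from 29,832 at ρ = 0.02 to 292 at ρ = 0.20. The size calculation is not in question. It is used in step 5 to price the fix.

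**2. Can the missing variables reach the model?** Set the sections side by side:

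- 8.3.3 does not list the agent stopped or ART status at index.
- The set named in advance in 8.5.1 contains neither.
- The screening clause in 8.5.1 draws on the descriptive analyses, which are defined by the lists in 8.3.2 and 8.3.3.

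No stated route brings either variable in. The advance set is introduced with the word including, so it is not strictly closed, but nothing in the text points to prior regimen.

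**3. What spread of previous regimens remains?** The bar in 8.3.1 removes the other core agents of interest once the patient is in OPERA. It leaves agents outside the list, such as EFV, ATV and LPV, and core agents used before OPERA entry. Previous regimens are fewer in kind but still mixed.

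**4. Possible size.** For a binary prior-treatment factor:

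bias = γ × Δp

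Here γ is the factor's effect on BMI change and Δp is the difference in its share between two agent groups. The protocol gives neither, so both are assumptions.

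| γ (kg/m²) | Δp = 0.10 | Δp = 0.20 | Δp = 0.30 |
|---|---|---|---|
| 0.1 | 0.01 | 0.02 | 0.03 |
| 0.3 | 0.03 | 0.06 | 0.09 |
| 0.6 | 0.06 | 0.12 | 0.18 |

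The comparison figures are the 12-month mean BMI increases in ART-experienced patients from the SCOLTA cohort cited in 6.1: DTG 0.30, RAL 0.24, EVG 0.23, DRV 0.41, RPV 0.06.

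- DTG − RAL = 0.30 − 0.24 = 0.06
- DTG − EVG = 0.30 − 0.23 = 0.07
- DTG − DRV = 0.30 − 0.41 = −0.11
- DTG − RPV = 0.30 − 0.06 = 0.24

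In absolute value these run from 0.06 to 0.24 kg/m². The largest assumed bias, 0.18, exceeds three of the four and is 0.18/0.24 = 75% of the fourth. The smallest, 0.01, is 0.01/0.06 = 17% of the smallest difference and 0.01/0.24 = 4% of the largest.

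**5. Power cost of adjusting.** Repeating step 1 with 15 or 20 covariates in place of 10 leaves the required N unchanged at the rows checked: 7,453 (ρ = 0.04), 3,309 (0.06), 1,858 (0.08) and 292 (0.20).

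**The case against.** The strongest reply has four parts.

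- **Recovery is partly covered.** The advance model includes change in viral load and CD4 count, which track recovery after a restart. Baseline viral load and CD4 count are listed in 8.3.3 and could enter through the screening clause. The stable-switch population is also described separately. This stands in part. Change in viral load and CD4 is only an indirect marker of ART status at index, viremia on a failing regimen is not the same as being off treatment, and the stable-switch objective is descriptive. None of these identifies the agent stopped.
- **The bar in 8.3.1 narrows the previous regimens.** This stands. It reduces the scope for confounding but does not remove it.
- **The model may be completed elsewhere.** The adjustment set is open-ended, and a separate analysis plan may name more variables. That is fair as to model detail. The covariate list, however, is fixed in the protocol and feeds the screening step, so the protocol is the place to add them.
- **The assumed range is wide.** It runs from negligible to the size of the cited differences. This stands, and it limits how strongly the point can be put.

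A reader might go further and infer from the background that the regimen left behind is already shown to matter. The documents do not support that. The finding that "patients prescribed ATV/r were less likely to experience a severe weight increase" comes from a randomized comparison in ART-naïve patients starting those drugs, not stopping them. Setting the 0.30 kg/m² gain on DTG beside the 5.3 kg gain after leaving EFV/TDF/FTC mixes two cohorts, 12 with 18 months, and DTG in general with one fixed combination. The cohort that left EFV/TDF/FTC held the previous regimen constant, so its differences are by destination.

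**Conclusion.** The point holds as a risk of residual confounding in the second primary objective. The protocol fixes a covariate list that omits the agent or class stopped and ART status at index, names no prior-ART variable for the model, and pools anyone with a history of ART.

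A reader might infer that the BMI comparison is in fact confounded. The documents do not show this, because they give no distribution of previous regimens by core agent.

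The size cannot be derived from the protocol. The range of 0.01 to 0.18 kg/m² rests wholly on the assumed effect (0.1 to 0.6 kg/m²) and the assumed imbalance (10 to 30 points). It makes no allowance for what change in viral load and CD4 already absorbs. The upper part of the range would matter against cited differences of 0.06 to 0.24 kg/m²; the lower end would matter little. The change is worth making because the bias is plausible and the cost is small.

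**What to change.** Make three changes:

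1. In 8.3.3, for ART-experienced patients, add the core agent or class of the regimen immediately before index, and whether the patient was on ART at index or restarting after a gap. Give each an unknown level.
2. In 8.5.1, name both in the set of variables chosen in advance for the BMI model and in the logistic model for the censoring weights.
3. Add a sensitivity analysis of the BMI comparison restricted to documented direct switchers.

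The cost is two derived variables and a few lines of protocol text. Length of previous regimen and number of classes already require earlier agents and dates to be identified, and section 8.4 reports 2.6 million ART prescriptions in the database. Required sample size is unchanged at the rows checked.

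The drawback is the unknown level. Patients classed as experienced only by a viral load below 1000 copies/mL have no documented ART history and will fall into it, as will others whose earlier treatment is not in the record. The number in that level should be reported by core agent, since a large or uneven share would limit what the adjustment can achieve.
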